This pilot RCT began data collection in May 2017 and continued through May 2018. A total of 45 youths and their families were recruited. Data was collected at four time points: baseline (recruitment), 1-month, 3-months, and 6-months. At baseline, caregivers completed a general information form on demographics and medical history, as well as measures to assess health status (Asthma Control Test), and health literacy (S-TOFHLA and Asthma Numeracy Questionnaire). Patients completed measures to assess health status (Asthma Control Test), health literacy (S-TOFHLA) and reading comprehension (WIAT-III), and complete pulmonary function testing (spirometry). Qualitative methods were used to gather acceptability and feasibility data. Participants in both groups were provided with their first canister or diskus of medication in order to attach the electronic adherence monitor at baseline. Participants refilled with medications they purchase as needed for the remainder of the study. One month after initial visit, families were called to complete the Asthma Control Test and study-specific satisfaction survey. Three months after initial visit, families returned to clinic for follow up with the physician and to complete the Asthma Control Test, AAP knowledge interview, and pulmonary function testing (patient only). Six months after initial visit, families returned to clinic for follow up with the physician and to complete the Asthma Control Test, AAP knowledge interview, satisfaction survey, spirometry (patient only), and to review adherence data and return the inhaler monitor. Six families completed follow up measures at 3 months due to time constraints.

The findings of this study will be relevant to research and practice with rural youths with asthma, as well as families with significant literacy issues. A novel and innovative stakeholder-led approach was used in this study to develop a more accessible and effective approach to asthma education in pediatric settings. The process and findings of this study will be widely disseminated and guide improvements to the PAAP for use in future research and practice, including the possible development of an "app" version of the PAAP.

Study Analysis Plan

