All analysis was conducted using SAS 9.4. Descriptive analysis was conducted on baseline measures for both the total sample, and by treatment group. Frequency and valid percentages were used to describe categorical data, means and standard deviations for continuous data, and medians and interquartile range for non-normal continuous data. Group differences were tested by chi-square, Fisher's exact, Mann-Whitney, or t-test as appropriate for variable type, with odds ratios (OR) and 95% CI of the OR, means by group and t-statistic, or mean score ranks and Z-statistic reported.

Generalized linear mixed model (GLIMMIX) with multinomial response distribution and a cumulative logit link function were used to analyze the daily adherence data, in order to model the ordinal outcome measure (0%, 25%, 50%, 75%, and 100% adherence) over time. Multiple covariance structure models were tested, with an unstructured matrix best fitting by AIC. Because adherence changed depending on prescription, the models were tested by both interaction of prescription and by stratification. Sensitivity analysis was also run for 3 months or less data and compared to the full 6 month dataset. Fixed effects were reported. Generalized linear mixed model (GLIMMIX) with binary response distribution was also conducted for the binary outcome of ACT cut-off ≥ 19 .

Linear mixed models with restricted estimation maximum likelihood estimation and Kenward-Richardson adjustment for the degrees of freedom were used for the continuous outcome data. Pre-post analysis included combining 3 month and 6 month time points for outcome measures where the final time point was 3 instead of 6 months. Time was treated as categorical for these pre- post- time points; otherwise time was treated as continuous variable. Time, Group, and Time by Group interaction effects were included in the model. Random effects statement included the time, with participants listed by ID. Different covariance structures and intercept inclusion were tests; AIC was used to determine best model fit with the best fitting model including no intercept and an unstructured covariance matrix. Fixed effects are reported. Sensitivity analysis was also run by including days in the study for those post-outcomes where some participants have 3 months or less data and compared to the full 6 month dataset.

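### The pre-post models enter some families' 3-month value as 'post' beside other families' 6-month value, so the Time by Group effect belongs to no defined time point

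*Combined protocol and SAP*

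**What the plan says.** On the schedule, the Methods section states: "Data was collected at four time points: baseline (recruitment), 1-month, 3-months, and 6-months". At the 3-month visit: "Three months after initial visit, families returned to clinic for follow up with the physician and to complete the Asthma Control Test, AAP knowledge interview", with spirometry for the child. The 6-month visit repeats these three measures and adds the satisfaction survey, which has no scheduled 3-month collection. On numbers: "A total of 45 youths and their families were recruited", and "Six families completed follow up measures at 3 months due to time constraints".

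The linear mixed model paragraph of the Study Analysis Plan gives the rule: "Pre-post analysis included combining 3 month and 6 month time points for outcome measures where the final time point was 3 instead of 6 months". In these pre-post analyses time is a two-level category; in the other models it is continuous. A sensitivity analysis adds days in the study for post outcomes where some participants have 3 months of data or less. The final paragraph takes the equivalence tests for continuous outcomes from the best-fitting mixed model.

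The plan does not say which outcomes were analysed pre-post, how the early enders fall between arms, how days in the study enters the model, or what happens to the 3-month value of a family that also has a 6-month value.

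**The concern.** Entering a final 3-month value in the slot that holds month 6 for everyone else is, in effect, last observation carried forward. The two visits are not interchangeable. By month 6 a family has had a further physician visit and three more months of refilling with medication it bought itself. Where AAP knowledge is the outcome, the 6-month interview also follows one scheduled at 3 months.

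Two consequences follow. First, if the PAAP-WAAP difference changes between 3 and 6 months, the merged effect is a blend, weighted by how many families stopped early. Second, if the early enders fall unevenly between arms, drift common to both arms passes into the treatment contrast. The merged result can also feed the equivalence test, and with it the claim that PAAP is as good as usual care.

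**Working it through.** The plan gives no figure to reproduce here: it states no sample-size calculation, assumed effect or SD.

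**Inputs from the documents.** 45 families, of whom six have follow-up at 3 months: 6/45 = 13.3%, leaving at most 39/45 = 86.7% with a 6-month value.

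**Assumptions, not in the documents.** Arms of 22 and 23; outcome SD of 1; a 3-to-6-month change d common to both arms, with 0.5 SD as the illustration.

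**1. Bias from common drift.** Let a of 22 and b of 23 children be early enders. Each lacks the change d, so the merged contrast shifts by d × (a/22 − b/23) in size. The arm with more early enders loses more of the change.

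| Split a/b | Calculation at d = 0.5 | Bias (SD) |
|---|---|---|
| 3/3 | 0.5 × (3/22 − 3/23) | 0.003 |
| 4/2 | 0.5 × (4/22 − 2/23) | 0.047 |
| 5/1 | 0.5 × (5/22 − 1/23) | 0.092 |
| 6/0 | 0.5 × (6/22 − 0) | 0.136 |

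The bias scales with d: at 6/0 it is 0.07 SD for d = 0.25 and 0.20 SD for d = 0.75.

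**2. How likely an uneven split is.** If stopping early is unrelated to arm, a follows a hypergeometric distribution (6 drawn from 45, of whom 22 are in one arm). The probability of 5/1 or worse, in either direction, is 0.187. The probability of 6/0 is about 0.02. The expected absolute bias over all splits at d = 0.5 is 0.04 SD.

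**3. Blending with an even split.** Take a 6-month effect of 0.5 SD, three early enders among 22 PAAP children, and no common drift. If the 3-month effect is 0.25 SD, the merged effect is (19 × 0.5 + 3 × 0.25)/22 = 0.47. If the 3-month effect is zero, it is (19 × 0.5)/22 = 0.43.

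**4. Price of separating the visits.** These are generalised least squares standard errors with visits at 0, 3 and 6 months, compound symmetry with correlation 0.6, and three early enders per arm without month 6:

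- merged post effect: 0.267 SD
- 6-month effect, visits separate: 0.281 SD; 0.281/0.267 = 1.05
- average of the 3- and 6-month effects: 0.235 SD; 0.235/0.267 = 0.88

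The ratio of about 1.05 holds for correlations from 0.4 to 0.8. If a common baseline mean is assumed, the cost at 6 months is 6 to 7% for correlations from 0.3 to 0.7 (at 0.5: 0.275 against 0.258).

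**The case against.** The strongest reply is that the effect is small. An expected bias of 0.04 SD compares with a standard error of about 0.27 SD. The 0.14 SD case needs a 6/0 split and a drift that the documents do not give, and it is still minor against an equivalence margin of one SD. This stands, and it limits the severity. It does not make the merged effect a 6-month effect.

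The second reply is that the days-in-study analysis addresses exactly these outcomes. It may. In an idealised noise-free two-visit model, letting days act on the post value removes the common-drift bias even at 6/0; entering days only as a main effect does not. The plan does not say which was done, and either way the main result stays merged.

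A reader might also infer that the other families' 3-month data are discarded. The documents do not establish this. A two-level pre-post factor leaves no obvious place for an intermediate visit, but combining could mean coding both visits as post. The models with continuous time could also use 3-month values, for example for ACT, which is scheduled at all four time points. The knowledge argument is likewise conditional: the Methods section lists no baseline knowledge interview, so a pre-post knowledge contrast is not shown to exist.

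**Conclusion.** The point holds in a limited form. For the outcomes handled pre-post, the plan's own rule puts two visits in one category, and the Time by Group effect has no defined time point. That follows from the text and needs no assumption.

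The size does rest on assumptions: arms of 22 and 23, a 0.5 SD common change, and early ending unrelated to arm. Under these the bias runs from about 0 to 0.14 SD and is expected to be about 0.04 SD in absolute terms. It could be larger on average if early ending depended on the plan received; the documents give no information on this. They support neither a claim that 3-month data were wasted nor a claim that the trial's conclusions are overturned. Severity is modest: this is worth correcting because the correction is cheap.

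**What to change.** For each pre-post outcome scheduled at both 3 and 6 months (ACT, AAP knowledge and spirometry, where so analysed), fit 3 and 6 months as separate categorical visits, with baseline where it was measured and an unstructured within-child covariance. Early enders then contribute their 3-month value as a 3-month value. Satisfaction falls outside this change.

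Report the 6-month PAAP-WAAP difference as the main estimate, since the Design section describes a 6-month comparison, with the 3-month difference alongside. The average of the two has a smaller standard error, but it is a half-and-half mix of the visits and should not replace the 6-month estimate. Keep the merged post analysis as a labelled sensitivity run. List the outcomes analysed pre-post, report early enders by arm, and state how days in the study enters its model.

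The cost is revised wording and a re-run of existing models, with no new data. The 6-month standard error rises by about 5% (6 to 7% with a common baseline mean), and there are a few more covariance parameters to estimate from 45 children.

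### The linear mixed model leaves baseline means free by arm, so Time by Group usually gives up precision that the baseline scores already collected could recover

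*Combined protocol and SAP*

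**What the plan says.** Under Design, participants aged 8 to 17 were randomised to a pictorial or a written plan. Under Methods, 45 families were recruited and "Data was collected at four time points: baseline (recruitment), 1-month, 3-months, and 6-months". Of baseline it says: "Patients completed measures to assess health status (Asthma Control Test), health literacy (S-TOFHLA) and reading comprehension (WIAT-III), and complete pulmonary function testing (spirometry". Caregivers also completed the ACT at baseline. ACT is listed again at months 1, 3 and 6, and spirometry at months 3 and 6.

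The linear mixed models paragraph of the Study Analysis Plan covers the continuous outcomes:

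- Fixed effects: "Time, Group, and Time by Group interaction effects were included in the model".
- Coding of time: "Time was treated as categorical for these pre- post- time points; otherwise time was treated as continuous variable". The pre-post analysis merges months 3 and 6 "for outcome measures where the final time point was 3 instead of 6 months".
- Covariance: "Random effects statement included the time, with participants listed by ID", with "the best fitting model including no intercept and an unstructured covariance matrix".
- The only term added in a sensitivity analysis is days in the study.

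ACT is named only in the preceding paragraph, where a model with "binary response distribution was also conducted for the binary outcome of ACT cut-off" is described. The plan does not say which continuous outcomes used which coding of time.

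**The concern.** A Group main effect beside Time by Group gives each arm its own baseline mean. If baseline was measured before the assigned plan could affect it, randomisation makes the two expected baseline means equal. Any observed baseline difference is then chance. Subtracting it in full, as a change-score contrast does, is usually not the most precise use of it.

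What is at stake is precision. Aim 1(c) hypothesises better asthma control and spirometry with the pictorial plan, and 45 families leave little precision to spare. The baseline scores needed for adjustment are already in hand.

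**Working it through.** **No stated figure to reproduce.** The documents give no power calculation, SD or baseline-to-follow-up correlation. The 45 is a recruitment count.

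**Inputs.** From the documents: 45 recruited, two randomised arms, the fixed effects above. Assumed: arms of 22 and 23; baseline SD 1 and follow-up SD k; correlation rho of 0.3, 0.5, 0.7 or 0.9; two-sided 5% level. Let a = 1/22 + 1/23 = 0.0889.

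**Step 1, the contrast as fitted.** With time categorical (pre, post) and an unstructured two-time covariance, Time by Group is the difference in mean change. This is exact with complete data and approximate otherwise. Its variance is (1 + k² − 2·rho·k)·a.

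**Step 2, the adjusted contrast.** With the baseline score as covariate the variance is k²(1 − rho²)·a, times 1 + 1/(45 − 4) = 42/41 = 1.0244 for estimating the slope on baseline.

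**Step 3, the difference.** Before the 42/41 factor, the first variance exceeds the second by (1 − rho·k)²·a. This is never negative and is zero only at k = 1/rho. So with 45 followed, adjustment can cost at most 2.4% of variance.

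**Step 4, equal SDs (k = 1).** The detectable difference (80% power) is SE × (t.975 + t.80), which is 2.867 × SE on 43 df unadjusted and 2.868 × SE on 42 df adjusted.

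| rho | SE, Time by Group | SE, adjusted | Variance ratio | Detectable difference (SD) |
|---|---|---|---|---|
| 0.3 | 0.353 | 0.288 | 0.67 | 1.01 to 0.83 |
| 0.5 | 0.298 | 0.261 | 0.77 | 0.85 to 0.75 |
| 0.7 | 0.231 | 0.216 | 0.87 | 0.66 to 0.62 |
| 0.9 | 0.133 | 0.132 | 0.97 | 0.38 to 0.38 |

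Example at rho 0.5: unadjusted variance 2 × 0.5 × 0.0889 = 0.0889; adjusted 0.75 × 0.0889 × 1.0244 = 0.0683; ratio 0.77. Simulating 20,000 trials per setting gave ratios of 0.663, 0.769, 0.876 and 0.972.

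**Step 5, unequal SDs and fewer followed.** Variance ratios at rho 0.3, 0.5, 0.7 and 0.9:

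- k = 0.8: 0.51, 0.59, 0.64, 0.62.
- k = 1.3: 0.82, 0.93, 1.01, 0.94.
- k = 1 with an assumed 36 followed (18 per arm, factor 33/32): 0.67, 0.77, 0.88, 0.98.

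**Step 6, if time was continuous.** Time by Group is then a slope difference, again with a free baseline. Removing the Group main effect multiplies its variance, under compound symmetry and before small-sample cost, by 0.70, 0.81, 0.90, 0.97 for four ACT visits and by 0.60, 0.73, 0.84, 0.95 for three spirometry visits.

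**Step 7, why the covariance matters for a constraint.** With categorical time, random time effects without an intercept still let baseline and follow-up correlate. With continuous time starting at 0, the same wording could mean a random slope only, which treats baseline as independent of follow-up. If the truth were compound symmetry, equating baselines under that working covariance would multiply the variance by 0.88, 1.45, 2.77 and 9.39 (four visits), with break-even near rho 0.35. The covariate form in Step 2 does not depend on that covariance.

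**The case against.** The strongest reply is that nothing is wrong with the analysis. Free baseline means are valid in a randomised trial, and the overall aim of this pilot is acceptability and feasibility. Collection is complete and the analysis is written in the past tense. A change of estimator now is post hoc, for a gain whose size depends on quantities the documents do not give. All of this stands. It limits the status and size of the gain, but does not remove it: the calculation uses data already collected, and its downside is bounded at about 2.4% of variance.

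Several stronger readings are tempting and are not supported:

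- **Bias or false positives.** A reader might infer that the reported contrasts are biased or that type I error is inflated. Neither follows from this choice; both contrasts are unbiased under randomisation.
- **ACT score in this model.** A reader might take it as given that ACT score was analysed by the linear mixed model. The plan names ACT only for the binary cut-off, so this is an assumption.
- **No gain when follow-up is more variable.** At an SD ratio of 1.3 the gain shrinks, but the multiplier is still 0.82 at rho 0.3.
- **A slope-only covariance was fitted.** A reader might infer this from the absence of an intercept. The plan does not establish it. An unstructured matrix has no content for a single random slope. Under the compound symmetry of Step 7, with 45 complete participants and four visits, a random-intercept model would beat a slope-only one by about 16 AIC units at rho 0.3 and 226 at rho 0.9, and the plan says intercept inclusion was compared by AIC. Step 7 is a reason to check, not a finding.
- **The equivalence test is impaired.** That test uses output from this model, but psi-squared compares the group and time-point means with an overall mean; it is not the Time by Group contrast. No effect on it is shown.

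**Conclusion.** The point holds as a low-cost improvement. In the pre-post fit, an unadjusted Time by Group contrast is valid but usually less precise than a baseline-adjusted one. With equal SDs, the variance saved runs from about a third at rho 0.3 to 3% at rho 0.9. It can be larger if follow-up scores vary less than baseline scores. At an SD ratio of 1.3 it ranges from about 18% saved to a loss of 1.5%.

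This rests on near-equal arms, on assumed correlations and SDs, on ACT score having been analysed as continuous (for ACT only), and on baseline having been measured before the assigned plan could affect it. Methods equates baseline with recruitment but does not give the order of measurement, randomisation and plan delivery. If spirometry is very stable between visits, its gain could be negligible.

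**What to change.** 1. Confirm that baseline ACT and spirometry were taken before the assigned plan could affect them. State which continuous outcomes used categorical and which used continuous time, and whether ACT score was among them.
2. For spirometry, and for ACT score if it was analysed as continuous, add a model of the follow-up score with the baseline score as covariate. Report it beside the existing analysis and label it post hoc.
3. An equal-baseline constraint (visit plus arm-by-post-baseline-visit terms, without a Group main effect) is an alternative only if the fitted covariance lets baseline and follow-up correlate.
4. Do not apply either form to the knowledge interview or satisfaction survey, for which Methods lists no baseline, or to the adherence model. No rerun of the psi-squared test is asked for.

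Cost: no new data, one further model per outcome, and at most about 2.4% of variance with 45 followed (about 3.1%, or 1/32, with 36).

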of pictorial & written AAPs. Our working hypothesis is that relative to usual care (Written AAP), Pictorial AAP will produce superior clinical and behavioral outcomes: (a) better treatment plan knowledge for caregiver and patient; (b) higher daily adherence rates to preventive medication (via electronic monitoring); and (c) better health outcomes (i.e., report of better asthma control & higher *lung functioning* or spirometry scores). This hypothesis is based in part on research findings indicating that use of pictures in health education markedly increases recall of information through simpler and more salient cues.

Specific Aim # 2 – Evaluate provider and family acceptability of pictorial AAP. Based on existing literature, we expect that the Pictorial AAP will be easy and user-friendly for providers to offer as well as patients and families to use. Consequently, our working hypothesis is that patient and caregiver satisfaction (e.g., perceived ease of use, benefits) survey scores will be significantly higher for the Pictorial AAP than for the Written AAP group.

Specific Aim # 3: Identify whether parent health literacy and youth literacy levels are associated with treatment outcome. Pearson (parametric) or Spearman (non-parametric) correlations will be used as appropriate to assess the association between parent health literacy and youth literacy to changes in knowledge, adherence, and health outcome, as well as caregiver and patient satisfaction, within and between AAP groups. Given that research suggests the use of graphics and images improves comprehension of medical information, it is anticipated that rural youth, particularly with lower literacy levels, will benefit significantly from a simpler, “image rich” pictorial AAP.

Design: Pilot Randomized Controlled Trial

Young people aged 8-17 were randomly assigned to one of two groups (pictorial vs. written AAP, i.e. usual care) for 6 months. The Written AAP (WAAP) group received a personalized, text-based AAP. The WAAP is consistent with national practice guidelines [5] and recommended as standard care for patients with asthma. The proposed study will use the written AAP published by the National Heart Lung and Blood Institute (NHLBI) (Available at: https://www.nhlbi.nih.gov/files/docs/public/lung/asthma_actplan.pdf). Providers (not researcher) completed the WAAP with the child's prescribed medications and specific asthma care regimen. The provider reviewed the WAAP with the child and caregiver.

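### The AAP knowledge comparison is not adjusted for child age or baseline reading and literacy scores, which costs precision and leaves chance imbalance uncorrected

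*Combined protocol and SAP*

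**What the plan says.** Aim 1(a) expects the pictorial plan to give "better treatment plan knowledge for caregiver and patient". On allocation, the Design section says only that "Young people aged 8-17 were randomly assigned to one of two groups"; the ratio, the arm sizes and any stratification are not given. The Methods report that "A total of 45 youths and their families were recruited".

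The baseline battery for patients includes "health literacy (S-TOFHLA) and reading comprehension (WIAT-III"). Caregivers also complete the S-TOFHLA and a demographics form. The knowledge interview appears in the 3-month and 6-month visit lists but not in the baseline list.

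The linear mixed model paragraph of the Study Analysis Plan gives the fixed effects: "Time, Group, and Time by Group interaction effects were included in the model". On the random side, "Random effects statement included the time, with participants listed by ID". The only further covariate is in a sensitivity analysis: "Sensitivity analysis was also run by including days in the study for those post-outcomes". Baseline group differences are tested, but no step carries them into an outcome model. Literacy is used in the Aim 3 correlations; age is not used in any analysis.

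The paragraph does not name the knowledge score. I take it to be one of the continuous outcomes, because daily adherence and the ACT cut-off are the only outcomes given other models.

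**The concern.** How well a child can state the contents of an action plan plausibly depends on age and reading ability, and this sample runs from 8 to 17 years. The Background's own case against text-based plans is that they are pitched at a 7th to 9th grade reading level, so the authors themselves expect reading ability to matter.

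A baseline score on the same measure would normally absorb stable differences between children. Here none is listed. If both knowledge interviews come after the plan is handed over, the format effect is a comparison between different children, and Time by Group does not remove differences present from the start.

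With 45 families, predictable spread that is left in the residual widens the confidence interval for the pictorial-minus-written difference. An age or reading gap that arises by chance also passes straight into the estimate. The variables that would address both are already in the dataset.

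**Working it through.** **Nothing to reproduce.** The plan gives no sample-size calculation, alpha, knowledge SD, age distribution or covariate-knowledge correlation. What follows is an illustration on stated assumptions.

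**Inputs.** From the documents: 45 participants, ages 8 to 17. Assumed: arms of 22 and 23; ages even over the ten integer years; two-sided 5% test; one post-treatment knowledge score per child; r, the correlation of the covariates taken together with knowledge, between 0.2 and 0.7.

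**Chance age imbalance.**
- SD of age = √((10² − 1)/12) = 2.87 years.
- SE of a standardised arm difference = √(1/22 + 1/23) = 0.298; in years, 2.87 × 0.298 = 0.86.
- Probability of a gap in mean age of at least 1 year: 24%; 1.5 years: 8%; 2 years: 2%. Probability of a gap above 0.5 SD: 9.4%.

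**What a gap does to the estimate**, giving age the whole of r.
- A 1-year gap is 1/2.87 = 0.35 SD of age. It shifts the knowledge difference by 0.35 × r = 0.07, 0.10, 0.17 or 0.24 SD for r = 0.2, 0.3, 0.5 or 0.7. All are below one SE (0.298 SD).
- A 0.5 SD gap shifts it by 0.10, 0.15, 0.25 or 0.35 SD. Only the last exceeds one SE.

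**Precision.** Variance removed is r². Two covariates cost about 2 × 1/41 = 4.9%, so the net variance factor is (1 − r²) × 1.049. The detectable difference at 80% power is (1.960 + 0.842) × 0.298 × √(1 − r²). The last two columns do not include the covariate cost.

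| r | Variance removed | Net variance factor | Detectable difference (SD) | Power for 0.8 SD |
|---|---|---|---|---|
| unadjusted | – | 1.00 | 0.84 | 76.5% |
| 0.2 | 4% | 1.01 | 0.82 | 78% |
| 0.3 | 9% | 0.95 | 0.80 | 80% |
| 0.5 | 25% | 0.79 | 0.72 | 87% |
| 0.7 | 49% | 0.53 | 0.60 | 96% |

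At r = 0.2 the two covariates cost slightly more than they return.

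**Reading that matters in one arm only.** Suppose reading correlates 0.5 with knowledge in the written arm and 0 in the pictorial arm. The common slope is about 0.25, so a single covariate removes 0.25² = 6%, not 25%. After the cost of two covariates the factor is 0.9375 × 1.049 = 0.98, close to no gain.

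**Type I error** (6,000 simulated trials per setting, age as the only covariate). Over all trials the unadjusted test rejects in 4.3% to 5.0%. Among trials with an age gap above 0.5 SD it rejects in about 7%, 15% and 24% for r = 0.3, 0.5 and 0.7, against about 5%, 5% and 4% with adjustment.

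**The case against.** The strongest reply is that the unadjusted analysis is valid. Randomisation puts chance imbalance inside the standard error, overall type I error stays near 5%, and a typical 1-year gap moves the result by less than one SE. This stands. A reader might infer that the Aim 1(a) result is biased, or that an observed difference is really an age effect; the documents support neither. The conditional error rates matter only for the roughly one trial in ten with a large gap, and mainly at the higher correlations.

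Second, the spread due to age and reading cannot be called large, since every correlation used here is assumed. This also stands.

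Third, the literacy rationale is partly about effect modification: low-literacy youth are expected to gain more from pictures. A common reading slope may then recover little. This weakens the case for WIAT-III more than the case for age.

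Fourth, Aim 3 already relates literacy to knowledge. It does so by correlation, which does not adjust the arm comparison, and it omits age.

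Fifth, silence on stratification does not show that there was none, and Aim 3's reference to changes in knowledge, with the pre-post wording in the analysis plan, may imply a baseline interview. If there was one, an age effect that is constant over time cancels in Time by Group. The text is ambiguous, so the absence of a baseline score cannot be stated as fact.

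Last, this is a pilot centred on acceptability and feasibility, with no designated primary outcome. That limits the weight of the point but does not remove it.

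**Conclusion.** The point holds as one of precision and of chance imbalance left uncorrected. The listed knowledge model omits age and the baseline reading and literacy scores, and nothing elsewhere in the plan supplies the adjustment. The unadjusted comparison is not invalid.

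The documents do not allow the size to be stated. On the assumptions above, the removable variance runs from 4% to 49%, less about 2% per covariate. In practice that is anything from no net gain at r = 0.2 to a detectable difference of 0.60 instead of 0.84 SD at r = 0.7. The gain from reading is at the low end if reading matters only for the written plan.

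A reader might also infer that the adjusted estimate should become the main result. The document is dated May 2020, data collection ended in May 2018 and the analysis is reported in the past tense, so promoting it now would be a change of analysis after the data were available.

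**What to change.** - **Patient knowledge:** add child age (continuous) and baseline WIAT-III reading comprehension as fixed covariates. State whether WIAT-III enters as a raw or an age-standardised score, because that determines its overlap with age.
- **Caregiver knowledge:** add caregiver S-TOFHLA.
- **Reporting:** give the adjusted pictorial-minus-written difference with its 95% CI, labelled as a covariate-adjusted analysis, beside the unadjusted result already described.
- **Baseline score:** state whether knowledge was measured before the plan was given. If it was, adjust for that score as well.
- **Randomisation:** state whether allocation was stratified, and on what.

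The cost is small: about 2 degrees of freedom in the patient model, simple imputation of any missing baseline score, and one extra line per knowledge outcome in the results. No new data are needed.
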